## **1.b. Association between fracture type, fracture trauma type and bone mineral density**

*First author:* [name]

*Co-authors:* (in random order) [name]; [name], [name]; [name], [name]; [name].

*Last author:* [name]

*Study design:* Prospective multi-center cohort study

*Participants:* Approx. 200 individuals aged 18-60 years

*Exposure:* Acute, non-pathological hip fracture (intra- and extracapsular) regardless of trauma level

*Study groups:* High and low bone mineral density; high and low trauma injuries.

*Aim:*

1. Analysis of association between bone mineral density at the time of hip fracture (DXA scan) and fracture type.

Statistical analysis of categorical data using Chi-square test.

2. Analysis of association between trauma type and fracture type.

Statistical analysis of categorical data using Chi-square test.

*Collected variables in the prospective study:*

Fracture pattern (femoral neck fracture – undisplaced and displaced; basocervical fracture; trochanteric fracture – stable and unstable; subtrochanteric fracture)

Type of trauma (other than low-energy, low-energy)

DXA scan at the time of the fracture

For adjustment:

Gender, age, BMI

Comorbidity, medication

Diet

Abuse – alcohol, drugs, tobacco, anabolic steroids

Socioeconomics (working capacity, type of living)

Fracture history (own and first-hand relatives)

Laboratory tests including hormonal status

Physical / functional level prefracture (New mobility score and others)

Health-related quality-of-life prefracture

*Hypotheses:*

There is no association between low BMD and displaced/unstable hip fracture

There is no association between higher trauma energy and displaced/unstable hip fracture.

There is an association when both low BMD and higher trauma energy exists and displaced/unstable hip fracture.

*Perspective/clinical relevance:*

To understand the interaction between trauma energy level and bone strength (as measured by DXA) and fracture type.

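### SAP 1.b sets a joint hypothesis on low BMD and higher trauma energy, but every analysis it names takes one factor at a time, and its two no-association hypotheses are not labelled as nulls or expectations

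*SAP*

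**What the plan says.** All of this stands in SAP 1.b.

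- **Hypotheses.** The first is "There is no association between low BMD and displaced/unstable hip fracture". The second is "There is no association between higher trauma energy and displaced/unstable hip fracture". The third is positive and joint: "There is an association when both low BMD and higher trauma energy exists and displaced/unstable hip fracture".
- **Purpose** (Perspective/clinical relevance): "To understand the interaction between trauma energy level and bone strength (as measured by DXA) and fracture type".
- **Aims.** There are two, each with one factor: "Analysis of association between bone mineral density at the time of hip fracture (DXA scan) and fracture type" and "Analysis of association between trauma type and fracture type". Under each stands the same single line of method: "Statistical analysis of categorical data using Chi-square test".
- **Study groups.** "High and low bone mineral density; high and low trauma injuries".
- **Adjustment.** A list of variables for adjustment is given (sex, age, BMI, comorbidity and others), but no model and no interaction term.

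Section 1.b gives no alpha, margin, confidence interval or rule for reading a non-significant result. It plans for about 200 participants. The protocol (Material and Method) projects 200 to 300, calls the study mainly descriptive and gives no power calculation.

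**The concern.** The question that motivates 1.b is whether the two factors act together. A test of BMD averages over trauma energy, and a test of trauma type averages over BMD. Neither can show whether patients with both factors differ from patients with one. Followed as written, the plan leaves its third hypothesis without an analysis.

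The wording of hypotheses 1 and 2 adds a second difficulty. The SAP does not say whether they are formal nulls or expected findings. If they are expectations, the only route to supporting them in the plan is a chi-square test that fails to reach significance, and such a result does not show absence of association. If they refer to overall associations, they generally cannot hold together with hypothesis 3.

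At stake is how the paper is read: an uninformative p-value could be taken as a finding, and the joint question could be answered by an analysis chosen after the data are seen.

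**Working it through.** **1. Hypotheses against named analyses.** The plan has no figure of its own to reproduce, so the first check is a comparison of texts.

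| Hypothesis | Factor(s) | Named analysis |
|---|---|---|
| 1 | low BMD | chi-square, Aim 1 |
| 2 | higher trauma energy | chi-square, Aim 2 |
| 3 | both together | none |

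**2. Do hypotheses 1 and 2 fit with 3?** Suppose the risk of a displaced or unstable fracture is r in three groups and r + e in patients with both factors. Then the overall BMD difference is e × (share of low-BMD patients who had higher-energy trauma). This is zero only if no low-BMD patient had such trauma. Example (assumed): r = 40%, e = 30 points, factors independent, higher-energy share 20%, 30% or 50%. The overall BMD difference is 30 × 0.2 = 6, 30 × 0.3 = 9, or 30 × 0.5 = 15 points. The same holds for trauma with the factors exchanged. So the pattern in hypothesis 3 implies overall associations, unless an opposite effect elsewhere happens to cancel them.

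**3. What a one-factor test can show.** Inputs: N = 200 (SAP) and 300 (upper end in the protocol). Assumed: two-sided 0.05, average risk p = 30%, 50% or 70%, splits 50/50, 30/70 or 20/80, no adjustment, and every fracture classifiable as displaced/unstable or not (1.b gives no such split for basocervical and subtrochanteric fractures).

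95% CI half-width = 1.96 × √[p(1−p)(1/n₁ + 1/n₂)].

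- Narrowest, N = 200: p = 0.3, 100 vs 100: 1.96 × √(0.21 × 0.02) = 12.7 points.
- Widest, N = 200: p = 0.5, 40 vs 160: 1.96 × √(0.25 × 0.03125) = 17.3 points.
- N = 300: 10.4 to 14.1 points.

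Power uses the unpooled normal approximation with risks p ± d/2, in both directions.

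| True difference | Power, N = 200 | Power, N = 300 |
|---|---|---|
| 15 points | 40-65% (missed in 35-60%) | 56-82% (missed in 18-44%) |
| 20 points | 64-89% | – |
| 25 points | 83-98% | – |

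Large differences would usually be found; moderate ones often would not.

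**4. What the joint question can yield.** Further assumed: low BMD (share b) and higher-energy trauma (share t) are independent, each 20%, 30% or 50%. The group sizes are Nbt, Nb(1−t), N(1−b)t and N(1−b)(1−t). For the interaction as a difference of risk differences, half-width = 1.96 × √[p(1−p) × Σ(1/n)] over the four groups.

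- b = t = 0.5, p = 0.3, groups of 50: 1.96 × √(0.21 × 0.08) = 25.4 points.
- b = t = 0.3, p = 0.5, groups 18/42/42/98: 33.0 points.
- b = t = 0.2, p = 0.5, groups 8/32/32/128: 1.96 × √(0.25 × 0.1953) = 43.3 points.

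| 95% CI half-width (points) | N = 200 | N = 300 |
|---|---|---|
| one factor only vs neither | 14-25 | 12-20 |
| both vs neither | 18-36 | 15-29 |
| interaction | 25-43 | 21-35 |

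At N = 200 the joint group has 200 × 0.2 × 0.2 = 8 to 200 × 0.5 × 0.5 = 50 patients. If the factors are negatively associated it is smaller: with an assumed odds ratio of 1/3, about 4 instead of 8 and about 37 instead of 50.

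**The case against.** **The first two hypotheses may be formal nulls.** A null is conventionally written this way, and the SAP nowhere says that p>0.05 will be reported as support. This stands as a possible reading. Against it, hypothesis 3 and both hypotheses in 1.a are worded as expected findings, so the list would mix nulls with an alternative without saying so. Whichever reading is right, hypothesis 3 still has no analysis.

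**The one-factor tests may answer exactly what was asked.** The SAP does not say that either factor has no effect on its own; it speaks simply of low BMD and of higher trauma energy. A reader might infer that the authors claim an effect only in combination, and that a significant overall test would wrongly refute them. The documents do not support that much. If overall associations are meant, a significant test correctly contradicts hypotheses 1 and 2, and the tension lies between them and hypothesis 3. The size of the supposed harm is also fragile. In the 40/40/40/70% example the overall BMD test is significant in about 10-58% of studies at N = 200 under independence, but in only about 6% (both shares 20%) to 35% (both shares 50%) with an odds ratio of 1/3 between the factors. Such a negative association is plausible from the protocol's Background, which contrasts patients with disease or functional limitation with apparently healthy patients in high-energy accidents.

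**A multivariable analysis was evidently intended.** The adjustment list suggests so, and a four-group chi-square is not excluded. But no model is named, and adjusting for covariates does not by itself estimate an interaction.

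**The study is mainly descriptive.** True, and it lowers the weight of the point. It also favours estimates with intervals over hypotheses that the tests cannot support.

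**Conclusion.** The point holds as a gap between question and method. SAP 1.b states a joint hypothesis and an interest in interaction and names no analysis for either. This rests on the text alone and does not depend on how hypotheses 1 and 2 are read. Their status is unclear; if they are expectations, non-significance cannot support them, and if they concern overall associations, they generally conflict with hypothesis 3.

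The figures only illustrate what about 200 patients can show: moderate overall differences are often missed, and the interaction is estimated very imprecisely. They rest on assumed alpha, risks, shares and independence, and the normal approximation is rough when the joint group has about 8 patients. A reader might conclude that the SAP plans to report non-significance as proof of no association; it does not say that. Severity is low: a cheap improvement.

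**What to change.** In SAP 1.b:

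1. Add a third aim. Report the proportion of displaced or unstable fractures in the four groups formed by the SAP's own study groups: neither factor, low BMD only, higher-energy trauma only, both. Compare each of the last three with the first, with a 95% CI. Give one BMD-by-trauma interaction estimate with a 95% CI, on a scale (risk difference or odds ratio) fixed before analysis. The same interaction can be carried into any adjusted analysis.
2. Label hypotheses 1 and 2 as formal nulls or as expectations.
3. State that p>0.05 will not be reported as evidence of no association.

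The cost is a few lines of SAP text, one table and one estimate, all from variables already collected; no new patients or measurements are needed. The table requires a decision on how basocervical and subtrochanteric fractures are classified. The downside is that the four-group and interaction intervals will be wide, so the conclusions will be more modest.

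### SAP 1.b names only two unadjusted chi-square comparisons, so its joint hypothesis (low BMD together with higher trauma energy) and its adjustment list have no method

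*SAP*

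**What the plan says.** SAP 1.b has two aims. The first is "Analysis of association between bone mineral density at the time of hip fracture (DXA scan) and fracture type". The second is "Analysis of association between trauma type and fracture type". Each is followed by the same line, "Statistical analysis of categorical data using Chi-square test", and no other method is named in 1.b. The groups are given one factor at a time: "High and low bone mineral density; high and low trauma injuries".

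Three hypotheses follow. The first is "There is no association between low BMD and displaced/unstable hip fracture". The second says the same of higher trauma energy. The third concerns the combination: "There is an association when both low BMD and higher trauma energy exists and displaced/unstable hip fracture". The closing Perspective item gives the interaction of trauma energy and bone strength as the purpose of the paper.

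Under the heading "For adjustment" stand nine lines of variables, from sex, age and BMI through comorbidity, diet and laboratory tests to prefracture quality of life. The planned size is about 200.

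The protocol (Material and Method) announces a risk factor analysis for sustaining a hip fracture and for complications and re-operations. It does not mention fracture type as an outcome and names no model.

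**The concern.** Hypotheses 1 and 2 match the two aims. Hypothesis 3 matches neither, and a two-way chi-square test has no place for covariates. The part of the paper closest to its stated purpose is therefore the part without a method.

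Three consequences follow if 1.b is carried out as written:

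- Nothing in it can confirm or refute hypothesis 3, or describe the interaction.
- If BMD and trauma energy are related in this cohort (the documents do not say), each two-way test can be confounded by the other factor.
- Hypotheses 1 and 2 assert no association, so two non-significant tests could be read as confirming them.

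A smaller point concerns the outcome. The fracture list reads in part "undisplaced and displaced; basocervical fracture; trochanteric fracture". Neck fractures are split by displacement and trochanteric fractures by stability, but 1.b does not say how basocervical and subtrochanteric fractures enter the displaced/unstable class. The protocol refers to standardised radiograph definitions that are not shown, so this may be settled elsewhere.

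**Working it through.** The plan gives no power, alpha or effect size for 1.b, so there is no figure to reproduce. The gap itself is a matter of text. The calculations below show whether the two planned tables could stand in for the missing analysis, and how precise the missing analysis would be.

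**Inputs.** N = 200 comes from the SAP. Cell sizes, risks of a displaced/unstable fracture and two-sided alpha 0.05 are assumptions. Cell order throughout: neither factor / low BMD only / higher energy only / both.

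**1. Same margins, different answers (four cells of 50).** Each margin is the average of two cells. The interaction OR is odds(both) × odds(neither) / [odds(low BMD only) × odds(higher energy only)].

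| Risks, % | Each margin: with vs without factor | Interaction OR |
|---|---|---|
| 40/40/40/70 | (40+70)/2 = 55 vs (40+40)/2 = 40 | 3.50 |
| 32.5/47.5/47.5/62.5 | (47.5+62.5)/2 = 55 vs (32.5+47.5)/2 = 40 | 0.98 |
| 60/40/40/60 | (40+60)/2 = 50 vs (60+40)/2 = 50 | 5.06 |

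In 100,000 simulated studies of each of the first two patterns, the BMD chi-square test rejected in 58.9% and 58.4%. A Wald interaction test (0.5 added to each count) rejected in 57.4% and 5.0%. The planned tests barely distinguish the patterns. In the third pattern both margins are flat despite a strong interaction.

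The first row has a further implication. If hypothesis 3 holds because only the combination matters, the margins differ, and the planned tests would tend to reject hypotheses 1 and 2.

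**2. Both versus neither does not isolate the combination.** For the first two patterns the OR is (0.70/0.30)/(0.40/0.60) = 3.50 and (0.625/0.375)/(0.325/0.675) = 3.46.

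**3. Precision of the interaction.** SE of the log interaction OR = √Σ 1/[n·p·(1−p)] over the four cells. The 95% confidence factor is exp(1.96·SE), and power is Φ(ln 3.50/SE − 1.96). On the risk-difference scale, where the interaction is 70 − 40 − 40 + 40 = 30 points, the half-width is 1.96·√Σ p(1−p)/n. For 40/40/40/70%:

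| Cells | SE | Factor for OR | Power | Half-width, points |
|---|---|---|---|---|
| 50/50/50/50 | 0.588 | 3.2 | 57% | 27 |
| 60/60/56/24 | 0.642 | 3.5 | 50% | 28 |
| 48/72/64/16 | 0.712 | 4.0 | 42% | 31 |

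The best case is cells of 50 with every risk 50%: SE = √[4/(50 × 0.25)] = 0.566, factor 3.0.

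**4. Confounding, only if the factors are related.** Take cells 48/72/64/16, so low BMD occurs in 16/80 = 20% of higher-energy and 72/120 = 60% of low-energy patients. Let BMD have no effect. With baseline risk 20% and trauma OR 3, the higher-energy odds are 0.25 × 3 = 0.75, a risk of 42.9%. The low-BMD group then shows (72 × 20% + 16 × 42.9%)/88 = 24.2%, and the rest (48 × 20% + 64 × 42.9%)/112 = 33.1%. The apparent BMD OR is 0.64. Over baseline risks of 20–50% and trauma ORs of 2 to 3, the apparent OR runs from 0.64 to 0.77 and 13–31% of BMD tests reject. With unrelated factors this disappears.

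**5. A null result is not evidence of absence.** With 100 versus 100 patients, 40% risk in each and an observed OR of exactly 1.0, SE = √[2 × (1/40 + 1/60)] = 0.289, so the 95% CI is 0.57 to 1.76.

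**The case against.** The strongest reply is that hypothesis 3 need not mean a product term. Read literally, it says that patients with both factors have more displaced/unstable fractures. The study groups can be crossed into four, and a chi-square test can compare those. For 40/40/40/70% and the three cell splits above, a four-group chi-square has simulated power of about 90, 65 and 48%, and both-versus-rest about 97, 81 and 67%, against 57, 50 and 42% for the interaction test.

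This stands in part: a crossed table would be a minimum analysis for hypothesis 3. However, 1.b does not define that comparison, and it would leave the adjustment list unused. The extra power belongs to a different question. In the near-additive pattern, both-versus-rest compares 62.5% with (32.5 + 47.5 + 47.5)/3 = 42.5%. The expected z is 0.20/√[0.475 × 0.525 × (1/50 + 1/150)] = 2.45, so that test also tends to reject where there is essentially no interaction.

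Other points are fair:

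- The chi-square line is generic, and the adjustment heading shows that a further model was intended. Parts of both documents are not in the text available, so the finding is limited to what is visible.
- Every risk and cell size above is assumed. The finding about the text does not depend on them.
- The protocol calls the study largely descriptive. That explains the missing power calculation, but not a stated hypothesis without a method.

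**Conclusion.** The concern holds and should be fixed. In the available text of SAP 1.b, hypothesis 3, the interaction purpose and the adjustment list have no stated method, and the protocol does not supply one. The two named tests cannot fill the gap, because the same two-way tables are compatible with interaction ORs of 3.50 and 0.98.

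The harm is limited to what this one paper can conclude; no data collection is affected. The text finding is firm. The numerical illustrations rest on assumed cell sizes and risks, and the confounding example applies only if BMD and trauma energy are related in this cohort. How basocervical and subtrochanteric fractures are classed is a minor, secondary gap.

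**What to change.** Keep the chi-square tables as description and add to SAP 1.b:

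- **Model.** One pre-specified logistic regression of displaced/unstable (yes/no) on BMD group, trauma energy and their product, adjusted for age, sex and BMI from the SAP's own list. That is six terms. If 40–50% of 200 patients have the outcome (an assumption), there are 80–100 events, or 80/6 = 13 to 100/6 = 17 per term.
- **Outcome.** State beforehand how basocervical and subtrochanteric fractures are classed.
- **Fracture location.** Site is part of fracture type, so adjust for it only as a sensitivity analysis, with a coarse split (for example intracapsular versus extracapsular) in which each level contains both outcomes: seven terms, 11–14 events each. Four-site coding gives nine terms, 9–11 events each, and fails through separation if a whole site falls in one outcome class.
- **Reporting.** Give each factor's mutually adjusted effect from the model without the product, and the interaction on the odds-ratio and risk-difference scales, all with 95% CIs. Both-versus-neither may be added as a separate estimand, not as evidence that only the combination matters.
- **Interpretation.** Do not read non-significant results as showing no association for hypotheses 1 and 2.

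A four-group or trauma-stratified table with a homogeneity test would be the minimum for hypothesis 3, but would leave the adjustment list without a method.

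The cost is SAP wording and one model on data already planned. The drawback is the imprecision shown above: at about 200 patients the interaction can be estimated but may not be resolved.
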